**4.12 Removal of Subjects from Protocol Therapy**

Subjects will be removed from therapy when any of the criteria listed in [Section 5.5](#) apply. Notify the Principal Investigator, and document the reason for study removal and the date the subject was removed in the Case Report Form. The subject should be followed-up per protocol.

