**5.1.14.2 Post-treatment biopsy:**

A post-treatment biopsy will be performed at one year post treatment regardless of whether clinical indication (tumor growth >4mm, enhancement, etc.) is present or not.

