**5.1.16 Kidney function assessment:**

Kidney perfusion assessed by Renal scintigraphy scan performed at baseline and at one year post treatment.

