**5.3 Follow-up Procedures**

Subject will be followed at every six months (+/- 2 weeks) thereafter for five years after their first follow up at 1 month (+/- 1 week).

With every visit, patients will have:

- Physical exam including: vital signs, weight, height and BMI
- MRI with or without contrast or CT with contrast
- Renal scintigraphy scan at 1 year
- Hematology
- Serum Chemistries
- Urine Analysis
- Lab corollary blood draw at 1 month and six month
- Performance status
- Toxicity evaluation
- Tumor measurements

**\*Note:** Subjects who show progressive disease or develop a new primary will be followed for survival only and will no longer strictly adhere to study calendar.

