## 5.5 Removal of Subjects from Study

Subjects can be taken off the study treatment and/or study at any time at their own request, or they may be withdrawn at the discretion of the investigator for safety, behavioral or administrative reasons. The reason(s) for discontinuation will be documented and may include:

- 5.5.1 Subject voluntarily withdraws from treatment (follow-up permitted);
- 5.5.2 Subject withdraws consent (termination of treatment and follow-up);
- 5.5.3 Subject is unable to comply with protocol requirements;
- 5.5.4 Subject demonstrates disease progression (follow-up permitted)
  - 5.5.4.1 Tumor size >4cm
  - 5.5.4.2 Loco-regional progression as defined in AJCC 7; stage >T1a.
- 5.5.5 Subject experiences toxicity that makes continuation with the remaining SABR fractions unsafe;
- 5.5.6 Treating physician judges continuation on the study would not be in the subject's best interest;
- 5.5.7 Subject becomes pregnant (pregnancy to be reported along same timelines as a serious adverse event) prior to the completion of SABR treatments;
- 5.5.8 Subject becomes unable to undergo imaging studies after enrollment, subject will be either replaced or withdrawn from study based on investigator's assessment;
- 5.5.8 Development of second malignancy (except for basal cell carcinoma or squamous cell carcinoma of the skin) that requires systemic treatment which could interfere with this study;
- 5.5.9 Lost to follow-up. If a research subject cannot be located to document survival after a period of 2 years, the subject may be considered "lost to follow-up." All attempts to contact the subject during the two years must be documented and approved by the Data Monitoring Committee.

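### The follow-up note in 5.3 moves patients with progression or a new primary to survival-only follow-up, which conflicts with the one-year biopsy and renal scan required elsewhere and can leave those secondary outcomes missing in relation to outcome

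*Protocol*

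**What the plan says.** Protocol section 5.3 (Follow-up Procedures) ends its visit list with a note which states that "Subjects who show progressive disease or develop a new primary will be followed for survival only". The note adds that strict adherence to the visit calendar then ceases.

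Other sections treat the same patients differently:

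- **5.1.14.2:** "A post-treatment biopsy will be performed at one year post treatment regardless of whether clinical indication" is present or not. Growth and enhancement are its examples of an indication. Sections 6.2 and 8.1.2 also call this biopsy required, and 6.2 bases pathologic response on it.
- **5.1.16:** "Kidney perfusion assessed by Renal scintigraphy scan performed at baseline and at one year post treatment". The Time and Events Table (5.4) shows the scan and the biopsy at one year with no exception for progression.
- **4.12:** "Subjects will be removed from therapy when any of the criteria listed in" 5.5 apply, and then "The subject should be followed-up per protocol".
- **5.5.4:** the criterion reads "Subject demonstrates disease progression (follow-up permitted"), with "Tumor size >4cm" and stage above T1a as its sub-items. The scope of the permitted follow-up is not stated.
- **4.11:** after growth, imaging continues at an interval set by the physician.
- **7.2.1, Late Adverse Events:** the late window runs to 3 years after treatment but appears to close at progression or death if either comes sooner.

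**The concern.** One-year pathologic viability (2.2.4) and change in renal perfusion and function (2.2.3, 2.4.2.4) are named secondary outcomes. If progression cancels the visits that measure them, the data are missing because of how the patient did. A patient who progresses before one year is more likely than others to have viable tumour, so a viability rate among biopsied patients would tend to look too favourable.

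Toxicity is affected as well. Sections 4.9 and 6.1.1 make every treated patient evaluable for toxicity, and section 1.3 notes that renal radiation injury can develop slowly. Survival-only follow-up contains no toxicity visit.

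Visit schedules belong in the protocol, so a statistical analysis plan cannot settle which passage governs.

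**Working it through.** **1. The passages side by side, for a patient declared progressive at the 6-month scan**

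| Item | 5.3 note | Other sections |
|---|---|---|
| One-year biopsy | not part of survival-only follow-up | required (5.1.14.2, 6.2, 8.1.2) |
| One-year renal scan | not part of it | scheduled (5.1.16, 5.4) |
| Six-monthly toxicity visit | not part of it | scheduled (5.4) |
| Imaging | not part of it | continues after growth (4.11) |

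The biopsy and scan are lost only if progression is declared before they are done. In practice that means at the 6-month scan, or at the one-year scan if it is read first. Later progressors lose toxicity visits and laboratory tests.

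**2. Who triggers the note**

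Under 6.1.4.1, progressive disease needs an increase of more than 20% and at least 5 mm over the nadir. Sections 2.4.2.3 and 5.5.4 add size above 4 cm or stage above T1a. Local failure in 6.1.4.1 is growth of at least 4 mm (or more than 2 mm on two consecutive scans), or any evidence of viability. The two groups overlap but differ. A local failure without progression stays on the calendar, while a patient with a new primary can leave it without local failure.

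**3. The plan's own figures (section 9.2)**

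Standard error at 90% local control and N = 16: √(0.9 × 0.1 / 16) = 0.075, as stated. The normal half-width is 1.96 × 0.075 = 14.7%, stated as 15%. Expected failures at 10%: 16 × 0.10 = 1.6. At the cited 3/34: 16 × 3/34 = 1.4. These are local failures of any kind, not progressions before one year.

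**4. How many could progress by size at 6 months**

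A 5 mm increase in half a year is a rate of 0.5 / 0.5 = 1.0 cm/year. Take the SD of 0.36 cm/year from 9.2 and assume normality:

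- Mean 0.16: z = (1.0 − 0.16)/0.36 = 2.33, probability about 1%, or 0.16 of 16 patients.
- Mean 0.4 (untreated): z = (1.0 − 0.4)/0.36 = 1.67, probability about 5%, or 0.8 of 16.

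New lesions, size above 4 cm and new primaries could add cases. A planning range of about 0 to 2 is reasonable, but it is an assumption.

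**5. Effect on observed viability**

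Let k early progressors go without biopsy, a of them with viable tumour, and let v of the other 16 − k have a viable biopsy. Observed rate: v/(16 − k). Rate with complete data: (v + a)/16. The observed rate is too low whenever a/k exceeds v/(16 − k). With a = k and v = 0:

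| k | Observed (exact 95% upper limit) | Complete (exact 95% upper limit) |
|---|---|---|
| 1 | 0/15 = 0% (21.8%) | 1/16 = 6.25% (30.2%) |
| 2 | 0/14 = 0% (23.2%) | 2/16 = 12.5% (38.3%) |
| 3 | 0/13 = 0% (24.7%) | 3/16 = 18.75% (45.6%) |

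The case k = 3 lies beyond both the planning range and the 1.6 failures expected, and is shown as an upper end.

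**The case against.** The strongest reply has five parts.

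- **Section 4.12 need not contradict 5.3.** It concerns removal from therapy, and following a patient per protocol can include the note itself. Permitted follow-up in 5.5.4 is satisfied by survival follow-up, and no longer adhering strictly to the calendar is softer than a full stop. This stands, so the conflict with 4.12 and 5.5.4 is the weaker part. The conflict with the required biopsy and the scheduled scan remains, because survival-only follow-up includes neither.
- **Tissue may exist anyway.** Section 6.1.4.1 recommends a biopsy for growth of at least 4 mm without radiographic viability, and for any radiographic viability. This reduces the loss but does not remove it: a recommendation is weaker than a requirement, and nothing says such tissue replaces the one-year result.
- **The late adverse event window in 7.2.1 itself appears to end at progression.** Section 7.2 also follows existing events to resolution. A reader might infer that the 5.3 note alone causes the loss of late toxicity data. The documents do not support that, and editing 5.3 alone would not cure it.
- **The group is not the set of patients who failed.** A reader might infer that data vanish in exactly the local failures. Step 2 shows otherwise.
- **Larger contrasts are hard to justify.** A reader might add viable biopsies among non-progressors, for example 2 early progressors plus 2 others: 2/14 = 14.3% observed against 4/16 = 25.0%. Any viable biopsy is already a local failure under 6.1.4.1, so this assumes 4 failures where the protocol expects at most about 1.6.

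**Conclusion.** The inconsistency is real and should be corrected. As written, the 5.3 note makes one-year viability and renal perfusion missing in relation to outcome for anyone whose progression is declared before the one-year assessments, and it ends scheduled toxicity visits for later progressors.

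The absolute size is small: probably 0 to 2 patients, each worth 1/16 = 6.25 percentage points. In the illustration the observed rate is 0% against 6% to 19%. That rests on assumed counts, on every early progressor having viable tumour, on no biopsy being taken, and on no viable biopsy elsewhere. The exact intervals at this sample size are wide in every case. The likely direction is downward for viability; the documents give no basis for a direction in the renal data.

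A reader might infer that the primary result is biased. The documents do not support that for its growth component, since most patients with size progression already count as local failures through growth. No sample-size figure changes.

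The range of 0 to 2 leaves out patients enrolled at 4 to 5 cm, whom section 3.1.2 admits and who already meet the size item in 5.5.4.1. That is a separate mismatch, but read literally it would widen the reach of the note to patients without local failure.

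**What to change.** Reconcile 5.3, 4.12, 5.1.14.2, 5.1.16, 5.5.4 and 6.2 with the late adverse event window in 7.2.1, so that one stated rule covers data collection after progression or a new primary. Specifically:

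- State that the move to survival follow-up does not by itself cancel one-year tissue, renal and toxicity data collection that is already scheduled, in patients who consent.
- Name tissue obtained for cause or at surgery as the pathologic result when it exists.
- Report renal function obtained after nephrectomy or ablation separately from data before it. Section 1.3 offers these treatments at any sign of progression, and pooling would mix their effect with that of the radiation.
- Align the late adverse event window with whatever rule is adopted.

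The cost is a few sentences across these sections and, for the roughly 0 to 2 patients who progress early, a few assessments already on the schedule. One of these is an image-guided multi-core biopsy, which is a real burden and needs the patient's agreement. Treatment, sample size and the primary analysis do not change.

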**5.4 Time and Events Table**

	Pre-study Within 2 months prior to registration	Day 1 First SABR	At One month (+/- 1 week)	q6 Months (+/- 2 weeks)	At one year (+/- 2 weeks)
Assessment	X				
Informed Consent	X				
Diagnostic/ Pre- treatment Renal Bx	X				
Post-treatment Renal Bx					X
Physical Exam	X	X	X	X	
Performance Status	X		X	X	
Toxicity Evaluations			X	X	
Tumor Measurements	X			X	

Chemistry	X		X	X	
CBC	X		X	X	
Correlative Labs	X	X*	X*	X*	
Urine Analysis	X		X	X	
MRI or CT	X			X	
Renal Scan	X				X

\*Correlative labs will be drawn at baseline, on first day of SABR (see section 8), at one month and at 6 month after SABR.

## 5.5 Removal of Subjects from Study

Subjects can be taken off the study treatment and/or study at any time at their own request, or they may be withdrawn at the discretion of the investigator for safety, behavioral or administrative reasons. The reason(s) for discontinuation will be documented and may include:

- 5.5.1 Subject voluntarily withdraws from treatment (follow-up permitted);
- 5.5.2 Subject withdraws consent (termination of treatment and follow-up);
- 5.5.3 Subject is unable to comply with protocol requirements;
- 5.5.4 Subject demonstrates disease progression (follow-up permitted)
  - 5.5.4.1 Tumor size >4cm
  - 5.5.4.2 Loco-regional progression as defined in AJCC 7; stage >T1a.
- 5.5.5 Subject experiences toxicity that makes continuation with the remaining SABR fractions unsafe;
- 5.5.6 Treating physician judges continuation on the study would not be in the subject's best interest;
- 5.5.7 Subject becomes pregnant (pregnancy to be reported along same timelines as a serious adverse event) prior to the completion of SABR treatments;
- 5.5.8 Subject becomes unable to undergo imaging studies after enrollment, subject will be either replaced or withdrawn from study based on investigator's assessment;
- 5.5.8 Development of second malignancy (except for basal cell carcinoma or squamous cell carcinoma of the skin) that requires systemic treatment which could interfere with this study;
- 5.5.9 Lost to follow-up. If a research subject cannot be located to document survival after a period of 2 years, the subject may be considered "lost to follow-up." All attempts to contact the subject during the two years must be documented and approved by the Data Monitoring Committee.

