**4.13 Subject Replacement**

The following are criteria for subject replacement: 1) If the subjects decide to withdraw from the study without finishing the course of SABR, 2) if the subjects decide to withdraw from the study or lost to follow up (for reasons of death from other causes, moving to other state etc.) or refuse follow up scans leading to <3 follow-up scans or <1 year of follow up, 3) if the subjects become unable to undergo an MRI or contrast enhanced CT scan with <1 year of follow up.

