### 6.1.1 Definitions

Evaluable for toxicity. All subjects will be evaluable for toxicity from the time of their first treatment with SABR.

Evaluable for objective response. Only those subjects who have measurable or non-measurable disease present at baseline, have received ALL fractions of SABR and have had their disease re-evaluated with a minimum of one year of follow up will be considered evaluable for response. These subjects will have their response classified according to the definitions stated below.

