## 9.0 STATISTICAL CONSIDERATIONS

### 9.1 Study Design/Study Endpoints

This is an open label single-arm phase II non-randomized prospective single arm study that treats a single SRM with SABR. The primary objective is local control of the SRMs. Local control is defined as less than 4mm increase in the longest diameter of tumor measured using either MRI or contrast enhanced CT scan and with no radiographic or pathologic evidence of viable tumor. The endpoint will be measured at a minimum follow up of one year. Secondary objections and endpoints explore the safety, toxicity, growth, growth rate, local failure, IDR, immune response and progression of the SRMs after SABR.

The stopping rules for this study include any treatment-related >grade 3 toxicity. If there are any treatment related grade 3 acute toxicity in >30% of enrolled patients after enrollment of at least 6 patients, the study will be suspended until permitted by a safety review.

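### Sections 5.5.8 and 4.13 give different rules for replacing a patient who can no longer be imaged, and neither bars replacing a documented local failure

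*Protocol*

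**What the plan says.** Two sections of the protocol deal with a patient who loses the ability to be imaged.

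- Section 4.13 (Subject Replacement) opens with "The following are criteria for subject replacement" and lists three items. Item 3 applies "if the subjects become unable to undergo an MRI or contrast enhanced CT scan with <1 year of follow up". Item 2 covers withdrawal, loss to follow-up and patients who "refuse follow up scans leading to <3 follow-up scans or <1 year of follow up".
- Section 5.5 (Removal of Subjects from Study) uses the number 5.5.8 twice. The first 5.5.8 covers a patient who can no longer be imaged at any point after enrollment: the "subject will be either replaced or withdrawn from study based on" the investigator's assessment. It does not refer to 4.13.

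Three other places matter.

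- Section 6.1.1 limits the response-evaluable set to patients who received all fractions and "have had their disease re-evaluated with a minimum of one year of follow up will be considered evaluable for response".
- Section 9.1 says "The endpoint will be measured at a minimum follow up of one year" and describes the trial with the words "This is an open label single-arm phase II non-randomized prospective single arm study".
- Section 6.1.4.1 defines Local Failure as Tumor Growth at a stated threshold (at least 4 mm in one scan, or more than 2.0 mm in two consecutive scans), or any radiographic or pathologic evidence of viability.

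**The concern.** A replacement rule in a small single-arm trial decides which patients make up the estimate. It should therefore be fixed in advance and should not depend on results. Here the same event is governed by two rules. One has a time window and no discretion. The other has discretion and no window. Because the trial is unblinded, whoever applies the second rule already knows the earlier scans.

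Neither section says what happens when failure was documented before imaging became impossible. A patient with a failing six-month scan can then leave the primary count and a new patient can take the place. There is no control arm in which the same selection would occur, so any such exchange acts directly on the local control rate.

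**Working it through.** **1. The two rules side by side**

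| | 4.13, item 3 | First 5.5.8 |
|---|---|---|
| Event | MRI or contrast CT no longer possible | Imaging no longer possible |
| Window | Under one year of follow-up | From enrollment, no end stated |
| Consequence | Replacement criterion is met | Replacement or withdrawal |
| Decided by | No discretion mentioned | Investigator, no criteria |

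They differ in two ways. Before one year, 5.5.8 makes replacement optional where 4.13 lists it as a criterion. After one year, 5.5.8 allows replacement where item 3 does not.

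**2. What is known when the choice is made**

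Section 5.3 schedules imaging every six months, and 5.1.14.2 requires a biopsy at one year. A patient who loses imaging after month six has at least one result on file. After one year the primary endpoint itself may already have been read.

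**3. What evaluability does**

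- Under one year, 6.1.1 makes the patient non-evaluable whichever option is chosen. A failure seen at six months then drops out of the count, and the choice in 5.5.8 decides only whether a substitute is enrolled.
- At or beyond one year, a re-evaluated patient is evaluable under 6.1.1. The protocol does not say whether replacing that patient removes the outcome.
- Item 2 of 4.13 has a related gap. It is met by fewer than three scans or by under one year. With six-monthly scans, a patient can reach one year with two scans, be evaluable under 6.1.1, and still meet the replacement criterion.

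**4. Size**

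Inputs from section 9.2: n = 16 and an expected local control rate of 90%.

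- The plan's own figure: SE = √(0.90 × 0.10 / 16) = 0.075, and 1.96 × 0.075 = 0.147. This reproduces the stated 7.5% and 15%.
- One patient: 1/16 = 0.0625, or 6.25 points. That is 0.0625 / 0.075 = 0.83 of the stated standard error.

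Illustration with exact (Clopper-Pearson) 95% intervals. The counts are assumptions.

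| Situation | Rate | 95% CI |
|---|---|---|
| 2 failures, both counted | 14/16 = 87.5% | 61.7 to 98.4 |
| One exchanged for a success | 15/16 = 93.8% | 69.8 to 99.8 |
| Both exchanged for successes | 16/16 = 100% | 79.4 to 100 |
| 3 failures, all counted | 13/16 = 81.3% | 54.4 to 96.0 |
| One of the 3 exchanged for a success | 14/16 = 87.5% | 61.7 to 98.4 |
| 2 failures, one replaced by a success but still counted | 15/17 = 88.2% | 63.6 to 98.5 |

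If one of two failures is withdrawn and not replaced, the rate is 14/15 = 93.3%. This is close to the 93.8% with a successful substitute. Most of the shift therefore comes from losing the documented failure, so deleting the investigator's choice would not be enough.

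**The case against.** The strongest reply is that the sections can be read together: 4.13 sets the criteria, 5.5 lists reasons for removal, and the investigator merely judges whether 4.13 is met. That reading is possible, but it is not written. The first 5.5.8 has no cross-reference, no time limit and no criteria. The reply reduces the point to a drafting mismatch, but it does not close the gap on documented failures, which lies in 4.13 itself.

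It is also fair to say that 6.points per patient is a property of n = 16 rather than of this clause, and that the illustration needs several things to happen together: a failing patient loses imaging, is replaced, is not counted, and the substitute succeeds. Both remarks stand, and the frequency of the event is not given. Sections 4.12 and 5.5 already require the reason for removal to be recorded, and 4.12 also the date, but not the last tumor status.

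Three stronger readings are tempting and are not supported.

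- A reader might infer that radiation damage to the kidney triggers the rule by ruling out contrast. Sections 5.1.15, 5.3 and 6.1.3 allow MRI without contrast, so renal decline alone does not trigger it.
- A reader might infer that the investigator can keep a patient who is doing well. Both options in 5.5.8 take the patient off study, and 6.1.1 decides evaluability.
- A reader might attach weight to the illustrated rate passing 90%. In 9.2 that figure is a planning expectation, not a success threshold, and 9.3 plans an estimate with an exact interval.

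**Conclusion.** The point holds in a limited form. The first 5.5.8 and 4.13(3) differ on discretion before one year and on whether replacement is possible after it. Neither bars replacement once Local Failure has been seen. Followed as written, the text allows a known early failure to leave a 16-patient estimate and a new patient to enter.

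The size is 6.25 points for each failure exchanged for a success, somewhat less than one stated standard error. This assumes that the exchanged failure is not counted. Before one year that follows from 6.1.1. After one year it is an inference, because no section says that replacement deletes an outcome already classified. The number of affected patients is unknown and may be zero. Nothing in the protocol suggests an intention to select patients; the rule simply leaves room for it.

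**What to change.** 1. In the first 5.5.8, delete the investigator's choice and refer to 4.13. Correct the duplicate number at the same time.
2. In 4.13, for items 2 and 3, add that a patient who has already met the Local Failure definition of 6.1.4.1 counts as a Local Failure in the primary analysis and is not replaced. Use the Tumor Growth threshold as defined there, or evidence of viability, so that smaller changes in size are not counted as failures.
3. In 4.13, add that a patient already evaluable under 6.1.1 is not replaced.
4. Align 6.1.1 so that a Local Failure documented before one year counts as evaluable.
5. Report every replaced patient with the last known tumor status.

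A cross-reference to 4.13(3) alone would not do, because that item still lets an early failure be replaced. The cost is a few sentences in three sections, with no added visits, scans or patients. One side effect should be acknowledged: early failures would be counted while patients lost early without failure are still replaced, which tilts the estimate slightly downward. The listing in step 5 lets a reader judge how much.
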